8. STATISTICS AND DATA ANALYSIS	20-23
9. DATA MANAGEMENT	23-24
10. ETHICAL AND REGULATORY CONSIDERATIONS	24-26
11. DISSEMINATION POLICY	26-27
12. SAFETY REPORTING	27
13. FINANCE AND INSURANCE	28
FLOW DIAGRAM OF PATIENT PARTICIPANTS THROUGH STUDY	29
FLOW DIAGRAM OF THERAPIST PARTICIPANTS THROUGH STUDY	30
REFERENCES	31-33

ii. List of Key Abbreviations

SVV: Subjective Visual Vertical

SCP: Scale for Contraversive Pushing

MRS: Modified Rankin Scale

NIHSS: National Institute for Health Stroke Scale

DC: Discharge

iii. Trial Summary

Study Title: Identifying vertical perception loss in people with acute stroke: A feasibility study.

Short Title: Feasibility of measuring vertical perception in acute stroke

Study Design: Cross sectional, feasibility study

Study Participants: Acute stroke patients in inpatient care

Planned Sample Size: As this is a feasibility study no planned sample size but up to 250 people could be screened for participation

Length of Participant Involvement: Equal to length of stay on the stroke unit

Planned Study Period: 01/03/24 – 31/8/24

Primary Objective: To establish the feasibility of completing the Catherine Bergego Scale, Scale for Contraversive Pushing (SCP) and bucket test in a clinical environment with acute stroke patients to assist with identification of vertical perception loss

Primary Outcome Measure:

The primary outcome is to understand the feasibility of completing the suite of outcome measures in an acute stroke setting:

- Proportion (%) of patients on whom the assessments are attempted.
- Percentage of patients who are able to complete all three assessments within four weeks of admission.
- Time taken to complete the three measures in an acute clinical setting
- A recommendation regarding the most feasible time point to complete these assessments.

Secondary Objectives:

To gain a further understanding of vertical perception loss in acute stroke patients.

Secondary Outcome Measures:

- An understanding of factors that prevent or facilitate completion of these three assessments
- An understanding of healthcare professionals' experiences of completing these assessments in an acute stroke unit.

- An understanding of whether people with stroke (or their advocates) find it appropriate to complete all three assessments in an acute stroke setting.
- Percentage of patients admitted to an acute stroke unit showing a positive test for vertical perception loss within four weeks of admission.
- To explore the relationship between vertical perception loss and:
 - Discharge destination
 - Care package size on discharge
 - Number of inpatient falls
 - Level of functional independence on discharge
- To explore if any elements of the Catherine Bergego Scale or Scale for Contraversive Pushing show a trend for a relationship to vertical perception loss

Primary Endpoint: Discharge from the stroke unit.

Intervention(s): Completion of three outcome measures as part of rehabilitation; Catherine Bergego Scale, Scale for Contraversive Pushing and Bucket Test

iv. Funding

Funder(s): There is no direct funding for this research

Financial support given: The University of Winchester pay all members of the supervisory team ([name], [name], and [name]) for their time supervising [name] throughout her PhD. They are not directly funding the research study itself.

Non-financial supporters: Royal Hampshire County Hospital are providing support by practitioners identifying potential patients, explaining the study to participants and obtaining written informed consent. The rehabilitation team on the stroke unit will also complete the outcome measures as part of routine therapy sessions.

v. Role of sponsor and funder

The members of the research team ([name], [name], [name] and [name]) are responsible for the design and management of the research. The funder/non-financial supporters themselves have not had a direct impact in the design or management of the research, but members of the research team are employed by them.

vi. Protocol contributors

All members of the research team have contributed to the protocol.

People with stroke known to the supervisory team will be asked prior to the study beginning to provide feedback on a lay summary of the proposed protocol, participant information sheets and consent forms with any recommendations considered and the documents adjusted if necessary.

vii. Keywords

Vertical perception; Stroke; Rehabilitation; Neglect; Pushing behaviour; Subjective visual vertical.

1. Background and Rationale

It is known that some people with stroke present with loss of vertical perception (Dai et al., 2021b, Utz et al., 2011, Perennou et al., 2008, Karnath et al., 2000). It has been established that loss of vertical perception is related to an inability to actively align the body with respect to gravity following stroke (Dai et al., 2022). It is measured using subjective visual vertical (SVV) (Perennou et al., 2008), subjective haptic vertical (SHV) (Utz et al., 2011) or subjective postural vertical (SPV) (Karnath et al., 2000). Furthermore, it has been associated with neglect (a disorder of spatial awareness whereby people with stroke fail to attend to their contralesional space/body) (Gammeri et al., 2020, Utz et al., 2011, Funk et al., 2010), and pushing behaviour (in which the patient uses their nonparetic extremities to push themselves to their paretic side leading to a loss of balance) (Bergmann et al., 2016, Karnath and Broetz, 2003). There is much debate about the terminology used to describe pushing behaviour (Nolan et al., 2022, Dai and Pérennou, 2021). This debate has led to a lack of a consistent approach to research, measurement tools and effective interventions to address this problem (Dai and Pérennou, 2021). A recent recommendation has been made that lateropulsion should be used to describe all those people that present with a tilted posture following stroke (Nolan et al., 2022, Dai and Pérennou, 2021). It could be argued that lateropulsion describes a wider range of those with stroke who are unable to align to vertical whereas pushing describes those at the more severe end of this spectrum. This argument is compounded by the different scales and cut off points used to identify pushing in research studies (Paci et al., 2023). Recently, the magnitude of visual vertical loss has been found to be related to that of lateropulsion (Dai et al., 2021b). It has been established that people with stroke that present with neglect or lateropulsion require longer periods of rehabilitation and have a worse functional outcome (Nolan et al., 2021, Babyar et al., 2015, Funk et al., 2011). Lateropulsion has been identified as the primary factor in disordered gait and balance after stroke (Dai et al., 2021a). This contributes to greater disability for the individual, safety concerns during rehabilitation and in the community, increases the burden on family and caregivers (Gomes-Osman and Kloos, 2021) and contributes to an estimated societal cost of £26 billion per year in the UK (Patel et al., 2019).

Identification of vertical perception loss early after stroke may be important in allowing identification of:

- Those who will require longer periods of rehabilitation
- Those who are likely to present with lateropulsion/pushing or neglect
- Those who may require more care and support on discharge

- Those with milder vertical perception loss who may be at risk of falling (Dai et al., 2021a), but do not have neglect or lateropulsion
- Changes in vertical perception over time
- Changes in vertical perception in response to rehabilitation interventions
- Those who will and will not respond to rehabilitation interventions and hence support appropriate allocation of therapy resources.

Currently, the established methods of measuring subjective vertical perception (visual, haptic or postural) are not feasible in the acute stroke environment (Piscicelli and Pérennou, 2017, Perennou et al., 2008). The main reasons are the equipment required being unsuitable in a clinical environment and the burden on the person with stroke. There is evidence that it is possible to use the more basic 'bucket test' to identify those with subjective visual vertical loss in the acute setting (Chang et al., 2019, Zwergal et al., 2009). Participants in these studies had central and peripheral vestibular disorders so is not translatable to the acute stroke population. Furthermore, some people with stroke who present with vertical perception loss present with normal visual vertical but a tilt in postural vertical (Karnath et al., 2000). Therefore, assessment of visual vertical alone may not identify all of those with vertical perception difficulties. As discussed, above vertical perception loss has been related to lateropulsion and neglect. Hence, the measurement of SVV, lateropulsion and neglect, is likely to be required to identify most people with vertical perception loss in the acute stroke setting.

The aim of this research is to establish the feasibility of using this suite of known outcome measures to identify those with vertical perception loss following stroke in the acute setting. If the use of these outcome measures is found to be feasible it will be the basis of further research to design and propose a reliable and valid method for measuring vertical perception loss in an acute stroke setting.

The principal research question that this study will aim to address is:

To establish the feasibility of completing the Catherine Bergego Scale (neglect) (Azouvi et al., 1996), Scale for Contraversive Pushing (SCP) (Karnath et al., 2002) and bucket test (SVV) (Zwergal et al., 2009) in a clinical environment with acute stroke patients to assist with identification of vertical perception loss.

The secondary research questions that this study will aim to address are:

- What percentage of patients admitted to an acute stroke unit show a positive test for vertical perception loss within four weeks of admission (evidence of subjective visual vertical (SVV) tilt on either bucket test or Catherine Bergego Scale or evidence of subjective postural vertical (SPV) tilt on SCP)
- For those able to complete the assessments, does vertical perception loss show any relationship with:
 - Discharge (DC) destination
 - Care package size on discharge
 - Number of inpatient falls
 - Level of functional independence on discharge
- Is there a trend for any element of the SCP or the Catherine Bergego to be more correlated with SVV tilt.

2. Objectives and outcome measures.

Primary objective:

To establish the feasibility of completing the Catherine Bergego Scale, the Scale for Contraversive Pushing (SCP) and the bucket test in a clinical environment with acute stroke patients, to assist with identification of vertical perception loss.

Primary outcomes:

The primary outcome is to understand the feasibility of completing the suite of outcome measures in an acute stroke setting:

- Proportion (%) of patients on whom the assessments are attempted.
- Percentage of patients who are able to complete all three assessments within four weeks of admission.
- Time taken to complete the three measures in an acute clinical setting
- A recommendation regarding the most feasible time point to complete these assessments.

Secondary outputs:

The secondary aims are to gain a further understanding of vertical perception loss in acute stroke patients.

- An understanding of factors that prevent or facilitate completion of these three assessments
- An understanding of healthcare professionals' experiences of completing these assessments in an acute stroke unit.
- An understanding of whether people with stroke (or their advocates) find it appropriate to complete all three assessments in an acute stroke setting.
- Percentage of patients admitted to an acute stroke unit showing a positive test for vertical perception loss within four weeks of admission.
- To explore the relationship between vertical perception loss and:
 - Discharge destination
 - Care package size on discharge
 - Number of inpatient falls
 - Level of functional independence on discharge
- To explore if any elements of the Catherine Bergego Scale or Scale for Contraversive Pushing show a trend for a relationship to vertical perception loss

3. Trial Design

This is a mixed methods feasibility study with data collected using a cross sectional design, focus groups and surveys. As the nature of acceptability is subjective a qualitative element utilising a phenomenological approach (Nicholls, 2009) will be nested into the study. This will allow an exploration of the experiences of professionals in completing or undertaking the outcome measures via focus groups. People with stroke (or their advocates) acceptability will be explored using a survey, a pragmatic approach to reduce the burden on research participants. Hence, a convergent mixed methods approach will be used (Creswell and Creswell, 2018) to fully answer the research aim and questions.

4. Trial Setting

The population to be studied will be acute stroke patients admitted to a stroke unit. A non-probability, convenience sample will be used. All patients with a diagnosis of stroke admitted for 72 hours to a single stroke unit at Royal Hampshire County Hospital will be considered in the present study.

Calculation of the sample size for a feasibility study is challenging (Hooper, Unknown). Sample sizes of between 24 and 50 participants have been recommended to allow calculation of a sample size for

a full-scale study (Sim and Lewis, 2012, Lancaster et al., 2004, Browne, 1995). Therefore a pragmatic approach to calculating the sample size will be taken. All those admitted to the stroke unit over a six-month period will be eligible for inclusion, meaning approximately 250 people will be screened for participation.

5. Participant Eligibility Criteria

Inclusion and exclusion criteria:

INCLUSION	EXCLUSION
Diagnosis of first stroke by stroke consultant based on clinical or radiographical findings	Under the age of 18
Admitted to stroke unit with a length of stay of over 72 hours	Diagnosis of Transient Ischaemic Attack (TIA)
Ability to consent or an advocate to consent on their behalf	Previous diagnosis of stroke or other neurological diagnosis affecting the brain with residual impairment
Pre-morbid Modified Rankin Scale of less than 4	Patients on an end of life pathway
	Patients with pre-morbid visual impairment that will not allow them to see the bucket test. Glasses can be worn.
	Inability to speak the English language and no interpreter can be found

6. Trial Procedures

Recruitment

All patients admitted to an acute stroke unit, who meet the inclusion criteria, may be invited to participate. Potential participants will be identified during the daily handover by members of the clinical or research team. Those meeting the inclusion criteria will be approached by a member of the research or clinical team and invited to participate. This will take place between 48 hours and one week after admission. Potential participants will be provided with the participant information sheet (PIS) regarding this study. If the patient is unable to consent due to cognitive or language impairment or low level of consciousness then their advocate will be approached. Where possible potential participants will be supported to consent using information in different formats (e.g.

through use of pictures) or the skill of appropriate members of the clinical team (e.g. speech and language therapists).

The number of people admitted to hospital with stroke who have language or cognitive impairments that may prevent them being able to consent is substantial. To exclude these potential participants would significantly impact the validity and generalisability of the results. Especially as those with significant strokes are more likely to present with vertical perception loss as well as cognitive and language impairment. If they were excluded a large number of patients with vertical perception loss may not be identified. These groups are often underrepresented in stroke research. If someone is unable to consent an advocate will be approached to consent on their behalf.

Those taking consent will decide on capacity. This includes the chief investigator and the stroke research nurse. Both have significant experience working with people with stroke. Both have undergone Good Clinical Practice training and Mental Capacity Act Training. If in any doubt about capacity other members of the healthcare team (e.g., Speech and Language Therapists) can give advice as to whether the potential participant has capacity or whether their advocate should be approached.

Participants will only be enrolled in the research if an advocate can be found to consent on their behalf. If someone lacks capacity and does not have an advocate they will be ineligible for inclusion in the research. Advocates will be identified through the medical records of the potential participant and will usually be their next of kin or other named contact. They will only be able to consent once they have read a PIS and had time to ask questions of the research team.

On reading the PIS if the patient or their advocate is willing to participate then they will be asked to sign a consent form, by the research team or chief investigator. Potential participants will have a minimum of 12 hours to read the PIS.

If a participant who lacked capacity, and was consented by an advocate, regains capacity then their informed consent to continue will be sought.

Study protocol

For those patients who consent, the qualified physiotherapists or occupational therapists on the stroke unit, will then attempt to complete all 3 outcome measures with the patient (see assessors and outcome measures below). If the patient is unable to complete any elements of the outcome measure for any reason, this will be recorded. If the patient is unable to complete the outcome measures, then an attempt will be made to complete the outcome measures at 1 week post

admission, if still unable they will be attempted again at 2 weeks and 4 weeks post admission. At the point participants complete all 3 outcome measures or at 4 weeks (whichever is earliest) most will have no further active participation in the quantitative part of the study. The assessments do not need to all be completed in one sitting and can be spread across sessions. If a patient is unable to be consented at 48 hours they will be consented as soon after this point as possible up to one week after admission, and this will be recorded. If patients are discharged or have a change in status following consenting to participate but prior to completion of the outcome measures any data collected to date will be utilised in the study results and the reasons for non-completion of the outcome measures will be noted as this will inform the feasibility of these outcome measures. The length of time taken to complete the measures will be recorded by the administrator. The expectation is that administration of all three outcome measures will take no longer than one hour. Due to the observational nature of the SCP and Catherine Bergego Scale elements of these can be completed during therapy sessions. The results and implications of the results of the outcome measures will be discussed with the patient or their advocate should they wish. The impact of the results on the therapists will be explored in a focus group.

At the point the participants are discharged from the stroke unit (this could include but not be restricted to: transfer to another rehabilitation facility, to undergo further neurological observation or intervention, discharge home, to undergo further unrelated medical interventions) their notes will be accessed and the following data extracted:

- Demographic details (age, gender)
- Type and location of stroke
- NIHSS on admission
- Number of in-patient falls
- Discharge (DC) destination
- Level of care required on DC – either care home or size of care package
- Functional ability on DC using the Modified Rankin Scale (MRS) (van Swieten et al., 1988) and the Barthel Index (Mahoney and Barthel, 1965) as these are routinely collected for all patients
- Amount of physiotherapy and occupational therapy received during inpatient stay as submitted to the Sentinel Stroke National Audit Programme (SSNAP). This includes minutes of therapy received per session of therapy, number of sessions of therapy per day and number of days on which therapy was received

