To identify trends for vertical perception loss and discharge status narrative statistics will be utilised. For instance the numbers of participants identified as having vertical perception loss who are discharged home will be investigated. If possible a Spearman Rank Correlation with Fisher-Z between outcome measure score and discharge information (e.g. length of stay in days, MRS score or Barthel Score) will be used. These tests have been chosen as the data is ordinal and are expected to be non-

parametric in nature. An ordinal regression will allow identification of which outcome measure is most likely to relate to discharge information.

A Spearman Rank Correlation with Fisher-Z will be completed on each element of the SCP and Catherine Bergego Scale against SVV to identify if any specific elements of the measures are more indicative of vertical perception loss than others. An ordinal regression will allow identification of which elements of the SCP and Catherine Bergego Scale are most likely to relate to SVV tilt.

The percentage of patients able to complete the measures, along with scores and confidence intervals for the outcome measures will be used to determine potential sample size for larger trials (Eldridge et al., 2016) and assess the change in vertical perception loss during in-patient admission.

It is known that neglect (Esposito et al., 2021) and pushing behaviour (Dai et al., 2022) improve over time. Therefore, changes in a sub-sample of the population will be tracked to inform future interventional research. For the subsample who have outcomes taken on discharge a Wilcoxon Sign Rank test will be used to identify the change in scores of the measures during in-patient stay. This will be completed for the whole study population and for each of the subgroups defined as mild, moderate or severe vertical perception loss.

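### Pre-stroke Rankin, residence and care package are not recorded, so the secondary analyses of discharge destination, care and function cannot separate existing dependence from new

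*Combined protocol and SAP*

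**What the plan says.** **Eligibility (section 5).** Inclusion requires a "Pre-morbid Modified Rankin Scale of less than 4", so grades 0 to 3 may enter. The exclusion nearest to this point is "Previous diagnosis of stroke or other neurological diagnosis affecting the brain with residual impairment". Disability from other causes, care-home residence and an existing care package are not exclusions.

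**Data extracted (section 6, Study protocol).** The baseline items are "Demographic details (age, gender"), type and location of stroke, and "NIHSS on admission". The discharge items include destination, "Level of care required on DC – either care home or size of care package", Rankin and Barthel. Falls and therapy amounts complete the list. No item describes the patient before the stroke.

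**Tabulation (section 8).** The participant table holds place of discharge, care needs on discharge, and discharge Rankin and Barthel. It has no pre-stroke counterpart for any of them.

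**Analysis (section 8).** For discharge status, "the numbers of participants identified as having vertical perception loss who are discharged home will be investigated". If possible, a Spearman correlation will relate measure scores to discharge information, and an ordinal regression will look for the measure most related to it. No covariate is named.

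**Rationale (section 1).** One reason given for early identification is to find "Those who may require more care and support on discharge".

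**The concern.** Section 2 lists four relationships of interest: discharge destination, care package size, inpatient falls and functional independence. For three of them (all but falls), the discharge value depends on what the patient was like before the stroke as well as on the stroke itself.

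A person who goes back to the same care home, or home with the same number of calls, enters the dataset exactly like a person who needs that care for the first time. The same applies to a discharge Rankin of 3 in someone who was already at 3. Admission NIHSS does not fill the gap, because it grades the stroke and not prior function, and section 8 does not adjust for it in any case.

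What is at stake is how these three relationships are read. The study is meant to be a basis for further work on measuring vertical perception loss, so a diluted or inflated signal could carry forward. The primary feasibility outcomes do not use these variables and are not affected.

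**Working it through.** The documents give no effect size, power or sample-size figure for these relationships, so there is no planned figure to reproduce. The check has two parts.

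**1. Search for any pre-stroke variable**

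| Place | Pre-stroke function or care? |
|---|---|
| Section 5, eligibility | Yes: pre-morbid Rankin, as an entry limit only |
| Section 6, extraction list | None |
| Section 8, participant table | None |
| Section 8, discharge analyses | None; no covariate named |

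Pre-morbid Rankin must be determined to apply the criterion, but it does not reach the listed data or the analysis.

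**2. What the gap could do (illustration; every input is an assumption)**

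- Half the participants have vertical perception loss.
- A share c had care before the stroke, and all of them have care at discharge: c = 10%, 20%, 30%.
- Among the rest, new care is needed with probability q: 20% or 40%.
- The odds ratio (OR) between prior care and loss is 1, 1.5, 2 or 3.

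*Share of discharge care that is pre-existing* = c / [c + (1 − c)q].
- Lowest: 0.10 / (0.10 + 0.90 × 0.40) = 0.10 / 0.46 = 22%.
- Highest: 0.30 / (0.30 + 0.70 × 0.20) = 0.30 / 0.44 = 68%.

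*Case A: prior care unrelated to loss (OR 1), true new-care risk 60% with loss and 20% without.*
Observed difference = [c + (1 − c)0.60] − [c + (1 − c)0.20] = (1 − c) × 40 points.
- c = 10%: 36 points
- c = 20%: 32 points
- c = 30%: 28 points

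With no true effect in this case, the observed difference is 0.

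*Case B: prior care associated with loss, and loss has no effect on new care.*
Let a and b be the proportions with prior care among those with and without loss, so that (a + b)/2 = c and [a/(1 − a)] / [b/(1 − b)] = OR. Observed difference = (a − b)(1 − q).
- Smallest (c = 10%, q = 40%, OR 1.5): a = 0.118, b = 0.082; 47.1% v 44.9%, a difference of 2 points, apparent OR 1.09.
- Middle (c = 20%, q = 20%, OR 2): a = 0.254, b = 0.146; 40.3% v 31.7%, a difference of 9 points, apparent OR 1.46.
- Largest (c = 30%, q = 20%, OR 3): a = 0.411, b = 0.189; 52.9% v 35.1%, a difference of 18 points, apparent OR 2.08.

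If the outcome is new care among those without prior care, Case A returns the true 40 points and Case B returns 0.

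**The case against.** **The route to a false positive is not obvious.** The Catherine Bergego items shown in the protocol score neglect of one side, the Scale for Contraversive Pushing scores lean and resistance towards the affected side, and the third measure is the bucket test. None is a general dependency scale. Requiring a first stroke and excluding earlier brain disease with residual impairment also removes obvious pre-stroke causes of a positive score. This stands. A link through age or frailty remains possible, but the documents neither show it nor rule it out.

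**Level or change is partly a choice of question.** Section 2 asks about care package size on discharge, which is a level, and the section 1 phrase can be read as more care than other patients need. This also stands: raw discharge values are legitimate and useful for discharge planning. But a level alone cannot show how much of the care is new, and that is needed before the relationship can be attributed to the stroke.

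**The analyses are exploratory and imprecise.** The text speaks of trends and of tests to be done if possible. Section 4 cites 24 to 50 participants as a recommended size. With 25 per group and proportions near 50%, the approximate 95% half-width is 1.96 × √(2 × 0.25/25) = 0.277, about 28 points, which is wider than any bias in Case B. The number enrolled is not fixed and could exceed 50. Even so, an interval displays sampling error, whereas nothing in the planned data would display this bias.

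**Pre-morbid Rankin should be recoverable.** It should, since eligibility depends on it. That makes it cheap to add. It does not put it in the analysis.

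**Conclusion.** The omission is confirmed. Followed as written, the plan cannot separate existing from new dependence in three of the four secondary relationships. The size is unknown. Under the assumed inputs above, a true 40-point difference falls to 28 to 36 points if prior care is unrelated to loss; if the two are associated at odds ratios of 1.5 to 3, a spurious difference of 2 to 18 points can appear.

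A reader might infer two stronger things, and the documents support neither:

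- *That the study will find a relationship where none exists.* This needs an association between prior care and vertical perception loss, for which the documents give no figure. Without it, the error is dilution.
- *That care-home residents and people with daily carers will be a known part of the sample.* The criteria do not exclude them. The documents do not say how many there will be.

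The point is worth acting on because the remedy is small and makes these relationships interpretable. It does not threaten the primary objective.

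**What to change.** 1. Add three fields to the extraction list in section 6 and the participant table in section 8: pre-morbid Rankin (already determined at screening) and, where the notes record them, pre-stroke residence and pre-stroke care package.
2. Keep the raw discharge values. Alongside them, report destination as returned to pre-stroke residence, new care home or other, and care as new or increased versus unchanged (yes/no).
3. In section 8, stratify the discharge analyses by pre-morbid Rankin, or include it as a covariate in the ordinal regression.

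A change in calls per day or a change in Rankin grade is not recommended. Section 8 codes care as nil, one to four calls, or 24 hour, with the number of carers, so a difference in calls has no clear value for 24-hour care, care homes or transfers to another facility. A Rankin difference treats ordinal grades as equal steps and leaves less room to worsen for those who start at 3.

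The cost is minor extra extraction at a notes review that already takes place, with no further patient contact. Some pre-stroke fields will be missing, because the protocol does not say that the notes hold residence and care. The counts of new care will be smaller than the counts of any care, and strata may be sparse.
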